7.2 Exclusion Criteria

Any subject who meets any of the following criteria will not qualify for entry into the study.

- 1. The subject has participated in another investigational study within 4 weeks (or based on local regulations) or within 5 half-lives of the investigational product before the screening visit. The 4-week or 5 half-lives window will be derived from the date of the last dose and/or AE related to the study procedure in the previous study to the screening visit of the current study.
- 2. The subject is an employee of the sponsor or study site or immediate family member (eg, spouse, parent, child, sibling) of the sponsor or study site.
- 3. The subject has a history of significant multiple and/or severe allergies (eg, food, drug, latex allergy) or has had an anaphylactic reaction or significant intolerance to prescription or nonprescription drugs or food.
- 4. The subject has a known hypersensitivity or contraindication to any component of TAK-510.
- 5. The subject has a positive pregnancy test or is lactating or breastfeeding.
- 6. The subject has a positive test result for hepatitis B surface antigen, hepatitis C virus antibody, or human immunodeficiency antibody/antigen, at the screening visit.
- 7. The subject had major surgery or donated or lost 1 unit of blood (approximately 500 mL) within 4 weeks before the screening visit.
- 8. The subject is unable to refrain from or anticipates using all medications including herbal medicines beginning approximately 7 days before administration of the first dose of study drug, throughout the study until 2 days after discharge.
- 9. The subject is unable to refrain from or anticipates using marijuana or cannabis-containing products beginning approximately 7 days before administration of the first dose of study drug, throughout the study until after the last PK dose.
- 10. The subject has a history or presence of alcoholism or drug abuse within the past 2 years prior to dosing, or frequent or heavy use (ie, near-daily) of medical or recreational cannabis in the past 3 months before screening.
- 11. The subject drinks alcohol in excess of 7 drinks/week for women or 14 drinks/week for men (where 1 drink = 5 ounces [150 mL] of wine or 12 ounces [360 mL] of beer or 1.5 ounces [45 mL] of hard liquor [45% alcohol]) within 3 months before screening.
- 12. The subject has a positive alcohol breath test or urine drug screen results at screening or check-in.
- 13. The subject has had a previous major psychotic disorder.

14. The subject has a history or presence of:

- 3 or more incidences of vasovagal syncope within the last 5 years prior to screening; or
- A family history of unexplained sudden death or channelopathy; or
- Brugada syndrome (ie, RBBB pattern with ST-elevation in leads V1-V3); or
- Cardiovascular or cerebrovascular disease, such as cardiac valvulopathy, myocardial infarction, stroke, sick sinus syndrome, pulmonary congestion, symptomatic or significant cardiac arrhythmia, second-degree atrioventricular (AV) block type 2, third-degree AV block, prolonged QT interval with Fridericia correction method (QTcF) interval, hypokalemia, hypomagnesemia, or conduction abnormalities; or
- Risk factors for Torsade de Pointes (eg, heart failure, cardiomyopathy, or family history of Long QT Syndrome); or
- Any clinically significant ECG findings or medical history including: long or short QTcF (over 450 msec or less than 360 msec), bifascicular block or QRS ≥ 120 msec or PR interval >210 msec at screening or Day -1 pre-Hour 0; or
- The subject has a documented history of sinus bradycardia (<45 bpm) based upon vital signs assessments, sinoatrial block as evidenced on ECG or sinus pause ≥ 3 seconds on ECG or predose telemetry.

15. The subject has an average semirecumbent BP less than 90/60 mm Hg or greater than 140/90 mm Hg from screening to predose, inclusive. Any assessments on Day -1, where 2 consecutive time point values do not meet this criterion, must be discussed with the medical monitor for approval.

16. The subject has an average HR <55 or >100 bpm from screening to predose, inclusive. Subjects with an average HR <55 bpm can be enrolled only with medical monitor approval. Any assessments after admission with an average HR <55 bpm, from Day -2 to predose (inclusive), will be left to the judgment of the investigator, unless HR is <50 bpm, which must be discussed with the medical monitor for approval.

17. The subject has orthostatic hypotension defined as a decrease in systolic BP ≥ 20 mm Hg or a decrease in diastolic BP ≥ 10 mm Hg at approximately 3 minutes of standing when compared with BP from the semirecumbent position at screening to predose assessments, inclusive. In asymptomatic subjects, any assessments after screening that do not meet this criterion may be repeated after the subject has remained in the semirecumbent or supine position for 15 minutes. If the repeat assessment is exclusionary based on the above criterion, the subject will not be eligible. If the repeat assessment is not exclusionary, the subject will be eligible.

18. The subject has postural orthostatic tachycardia, defined as an increase of >30 bpm or HR >120 bpm at approximately 3 minutes of standing, at screening to predose assessments, inclusive. Any assessments after screening that do not meet this criterion may be repeated with the subject remaining standing for up to a total of 5 minutes, provided that the subject remains asymptomatic. If the repeat assessment occurring within 5 minutes is exclusionary based on

the above criterion, the subject will not be eligible. A confirmed orthostatic increase of >30 bpm, but <40 bpm, on 1 or more Day -1 assessments may not be considered exclusionary if not considered clinically significant by the investigator and the medical monitor. Such assessments must be discussed with the medical monitor prior to determination that the subject is eligible to proceed.

19. The subject has a known or suspected current COVID-19 infection or is at risk of COVID-19 infection as assessed by the investigator.

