^a All BP and pulse assessments should be made in duplicate, and the average of both assessments should be used to calculate the final result. The investigator can take a third measurement if there is inconsistency (ie, a difference >10 beats per minute in heart rate or a difference >10 mm Hg in systolic or diastolic BP) between assessments (see Section 9.2.4 for details). If 3 measurements are obtained, the final BP readout should be the average of the 2 more consistent assessments. On Day -1, vital signs will be time-matched (±5 minutes) to the Day 1 clock time (ie, time-matched baseline). At predose, vital signs will be measured within approximately 1 hour before dosing.

^b For standing BP and pulse assessment, a BP and pulse assessment will be performed after the duplicate semirecumbent assessment has been completed. The subject should stand still for approximately 3 minutes before this assessment. Standing assessments must not be performed if semirecumbent systolic BP is <85 mm Hg or if the subject presents with signs or symptoms suggestive of postural hypotension after standing (eg, lightheadedness or dizziness, nausea, blurry vision). Day 1 time points will be time-matched (±5 minutes) to the Day -1 clock time (ie, time-matched baseline).

^c At least 24 hours of continuous telemetry monitoring will be conducted between check-in on Day -2 and predose on Day 1.

^d Predose time-matched telemetry extractions may take place between Day -2 and Day -1 in conjunction with the 24-hour predose continuous telemetry.

^e Collection of AEs will commence at the time the subject signs the informed consent form.

^f Only serum chemistry to measure electrolytes (sodium, potassium, chloride, and carbon dioxide) should be performed at the 4-hour assessment.

^g If CK is elevated in an individual subject after dosing, additional serum samples for CK may be collected at the investigator's discretion. The medical monitor will be updated regularly on any findings of elevated CK and plans for continued monitoring.

^h Hepatitis panel, including HBsAg and anti-HCV.

ⁱ Serum pregnancy test for female subjects only.

^j An FSH level will be obtained to assess postmenopausal status.

^k Urine PK samples will be collected at the following time intervals: predose, 0-4, 4-7, 7-12, and 12-24 hours.

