9.2.9.1 Hematology

Hematology will consist of the following tests:

Erythrocytes (red blood cells [RBCs])	Hemoglobin
Hematocrit	Platelets
Leukocytes (white blood cells [WBCs] with absolute differential)	

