9.2.9.2 Chemistry

Chemistry evaluations will consist of the following standard chemistry panel:

Albumin	Alkaline phosphatase
ALT	AST
Blood urea nitrogen	Calcium
Carbon dioxide	Chloride and lipase
Creatinine	Glucose
Gamma-glutamyl transferase	Sodium
Potassium	Bilirubin (total); if above the upper limit of normal, total bilirubin will be fractionated
Protein (total)	Creatine kinase

ALT: alanine aminotransferase; AST: aspartate aminotransferase.

If subjects experience ALT or AST $>3 \times$ ULN, follow-up laboratory tests (at a minimum, serum alkaline phosphatase, ALT, AST, total bilirubin, gamma-glutamyl transferase, and international normalized ratio) should be performed 24 hours after the abnormality was noted, and the medical monitor should be contacted. In Parts 2 and 3, if subjects experience ALT or AST $>3 \times$ ULN or total bilirubin $>2 \times$ ULN, laboratory tests for ALT and AST should be repeated before the next scheduled dose.

If ALT or AST remains elevated $>3 \times$ ULN, the investigator must contact the medical monitor for consideration of additional testing, close monitoring, possible discontinuation of study drug, and discussion of the relevant subject details and possible alternative etiologies. The abnormality should be recorded as an AE.

Please see Section 7.5 for subject discontinuation criteria regarding abnormal liver test results and Section 10.2.8.5 for guidance on reporting abnormal liver test results.

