9.2.9.3 Urinalysis

Urinalysis will consist of the following tests:

Protein	Glucose
Blood	Nitrite
Specific gravity	

Urine microscopy will be performed if urinalysis is abnormal. Microscopy consists of RBC/high-power field, WBC/high-power field, and casts.

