9.2.9.4 Diagnostic Screening

Other

Hepatitis B surface antigen	Hepatitis C virus antibody
HIV	FSH (for females only)
Serum pregnancy test (β hCG) (for females only)	Urine cotinine

β hCG: beta human chorionic gonadotropin; FSH: follicle-stimulating hormone.

Alcohol Screen

Subjects will undergo an alcohol breath test. A urine alcohol test may be performed at the discretion of the investigator.

Urine

The urine drug screening assessment will include the following tests:

Amphetamines	3,4-methylenedioxy-methamphetamine
Barbiturates	Methadone/metabolite
Benzodiazepines	Opiates
Buprenorphine/metabolite	Oxycodone/oxymorphone
Cannabinoids	Phencyclidine
Cocaine/metabolites	

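### Exclusion criterion 14 covers current hypomagnesemia, but no planned laboratory test measures magnesium, so an undiagnosed case with a clear history and an acceptable ECG cannot be detected

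*Protocol*

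**What the plan says.** Criterion 14 of Protocol Section 7.2 opens with "The subject has a history or presence of", so either a past or a current condition excludes. Its cardiovascular bullet ends with "prolonged QT interval with Fridericia correction method (QTcF) interval, hypokalemia, hypomagnesemia, or conduction abnormalities". Neither electrolyte disorder has a numeric limit. The same text stands in the Section 1.0 study summary.

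The laboratory sections define their panels as lists. Section 9.2.9.2 states: "Chemistry evaluations will consist of the following standard chemistry panel". The electrolytes in that panel are sodium, potassium, chloride, carbon dioxide and calcium. Sections 9.2.9.1 and 9.2.9.3 are framed in the same way ("Hematology will consist of the following tests"; "Urinalysis will consist of the following tests"), and Section 9.2.9.4 lists the diagnostic and drug screens.

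Eligibility also rests on other sources. Section 9.1.3 has site staff take a medical history. Inclusion criterion 6 asks the investigator to judge good health from history, examination, ECG, vital signs and safety laboratory results. A separate bullet of criterion 14 sets limits on QTcF, QRS and PR.

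**The concern.** The protocol fixes both the exclusion and the panel, and the two do not match. Of the paired electrolyte conditions, one can be checked against a scheduled result and the other cannot. Sites have to attest that hypomagnesemia is absent without a planned means of knowing.

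The exclusion sits among the QT and arrhythmia risks, and that is where the consequence would fall. ECG is part of the primary endpoint (Section 5.2.1), change from baseline in ECG parameters, QT/QTc included, is summarized (Section 11.1.4.4), increased heart rate is a named risk (Section 4.3), and 12-lead extractions are archived for a possible concentration-QT analysis (Section 9.2.6.2). If a rhythm or QT finding appeared after dosing, no scheduled result would show whether the subject had entered with low magnesium.

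**Working it through.** The protocol states no figure on this point, so the check is a comparison of the criterion with every place where a magnesium test could be listed.

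| Place in the Protocol | Content relevant here | Magnesium? |
|---|---|---|
| Section 9.2.9.1, hematology | red and white cells, hemoglobin, hematocrit, platelets | No |
| Section 9.2.9.2, chemistry | 17 analytes, including sodium, potassium, chloride, carbon dioxide, calcium | No |
| Section 9.2.9.3, urinalysis | protein, glucose, blood, nitrite, specific gravity; microscopy if abnormal | No |
| Section 9.2.9.4, diagnostic screening | hepatitis B and C, HIV, FSH, pregnancy, cotinine, alcohol, urine drugs | No |
| Table 9.a, specimens | PK, metabolite, immunogenicity and DNA samples | No |
| Tables 3.a to 3.j and footnotes | refer to the panels above, plus creatine kinase, liver tests and finger-stick glucose | No |

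Magnesium status is mentioned only as the excluded condition, in Sections 1.0 and 7.2. No redaction mark stands in the chemistry list. Some biomarker text elsewhere is blacked out, so the finding rests on the safety and screening lists, which are readable.

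Next, which routes can exclude a subject with low magnesium?

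1. **Known or past diagnosis.** Medical history (Section 9.1.3) records it, and the history half of criterion 14 excludes. This route works.
2. **ECG outside the limits.** QTcF over 450 or under 360 msec, QRS of 120 msec or more, or PR over 210 msec excludes whatever the cause. This route works, but it detects an ECG abnormality, not low magnesium. The protocol lists hypomagnesemia in addition to these limits.
3. **Investigator's judgment of good health.** It draws on safety laboratory results, which do not include this analyte, so it adds nothing for a silent case.
4. **Laboratory result.** For hypokalemia, potassium in the panel serves. For hypomagnesemia there is nothing.

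The remaining gap is current, undiagnosed hypomagnesemia in a subject with a clear history and an ECG within limits.

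The gap applies to every enrolled subject: 136 + 64 + 24 = 224 at most, before replacements. With 17 + 8 + 3 = 28 cohorts of 6 active and 2 placebo subjects (Table 6.a), 28 × 6 = 168 would receive TAK-510. These are the numbers not tested, not the numbers affected. The protocol gives no prevalence from which the latter could be derived.

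**The case against.** The strongest reply is that criterion 14 is largely a history criterion. Hypomagnesemia is one example in a list that also holds valvulopathy and stroke, with cardiomyopathy and family channelopathy in neighbouring bullets, and no echocardiogram, imaging or genetic test is scheduled for those. A named condition without its own confirmatory test is therefore not unusual here. This has force, and it is why rewording is an acceptable repair. It does not remove the mismatch: hypomagnesemia is defined by a laboratory value, its neighbour hypokalemia is covered by the panel, and the criterion expressly includes current disease.

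A second reply is that the protocol permits unscheduled procedures (Section 9.0) and gives urgent, nonscheduled safety evaluations precedence (Section 6.3.4). Magnesium could be measured when a rhythm finding occurs. That stands. A reader might infer that low magnesium could never be ruled in or out as a cause; the documents do not support this. What is lacking is the predose value for comparison.

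A third reply is that the planned results hardly depend on it. There is no formal inference (Sections 11.1.4 and 11.3), and exposure analyses of the telemetry ECGs, if done, are reported outside the study report. This also stands and limits the weight of the point.

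A reader might see the same fault in criterion 12 ("The subject has a positive alcohol breath test or urine drug screen results at screening or check-in"), because the schedules place no breath test at screening. That does not follow. The urine drug screen is scheduled at screening and at check-in, and every subject has a breath test at check-in on Day -2, before dosing, so the criterion can be applied. At most its wording could be tidied.

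**Conclusion.** The point holds as a minor inconsistency that is worth correcting. The protocol excludes current hypomagnesemia and plans no test that could find it, so an undiagnosed case with a clear history and an acceptable ECG would be enrolled, and no baseline magnesium would exist if a QT or rhythm finding followed.

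Two stronger readings should be avoided. A reader might conclude that any subject with this electrolyte risk passes all eligibility checks; the history half of the criterion and the ECG limits show otherwise. A reader might also multiply an assumed prevalence by 224 to count subjects dosed against the criterion. Such a prevalence is not in the documents, the product would ignore the history and ECG filters, and 224 includes placebo subjects (224 − 168 = 56).

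The conclusion rests on the laboratory lists being complete as printed. No endpoint definition, sample size or planned summary changes because of it.

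**What to change.** Reconcile criterion 14 (Sections 7.2 and 1.0) with Section 9.2.9.2 in one of two ways.

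- **Add the test.** Put magnesium in the chemistry panel, at least at screening and at the last safety laboratory before the first dose. The predose result has to be back before dosing if it is to serve eligibility; otherwise it serves only as a baseline. The serum is already being drawn, so no visit is added. The cost is a small assay charge and possibly a few more screen failures.
- **Reword the criterion.** Limit it to a known history of hypomagnesemia, so that it does not imply a test that is not done. This costs nothing, but leaves undiagnosed cases undetected and provides no baseline value.

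The first option is preferable, because it lets the sponsor's own exclusion be applied as written and supplies the baseline.

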7.3 Excluded and Allowed Concomitant Medications, Supplements, and Dietary Products

7.3.1 Concomitant Medications

The use of concomitant medications approximately 7 days before administration of the first dose of study drug, throughout the study until 2 days after discharge is not permitted. Subjects must be instructed not to take any medications without first consulting with the investigator. Any concomitant medication use must first be discussed with the sponsor, unless the investigator or designee considers immediate administration is necessitated.

The occasional use of acetaminophen (approximately <1 g/day) is allowed.

7.3.2 Fruit Juice

Subjects will refrain from consuming grapefruit juice, grapefruits, and products containing grapefruit beginning approximately 2 weeks before administration of the first dose of study drug, throughout the study, and until the last PK sample has been collected.

7.3.3 Alcohol

Subjects will refrain from consuming alcohol, 24 hours before admission until the final PK sample has been collected. Subjects may undergo an alcohol breath test at the discretion of the investigator.

7.3.4 Caffeine

In Part 1, subjects will refrain from consuming caffeinated beverages from the evening of Day -2 until the PK blood sample at 30 hours after dosing in each cohort. At all other times in Part 1 and in Parts 2 and 3, caffeinated beverages or xanthine-containing products will be limited to amounts of no more than 6 units per day (1 unit = 120 mg of caffeine).

7.3.5 Smoking

Subjects will abstain from the use of tobacco- or nicotine-containing products from screening until discharge after the last scheduled dose.

7.4 Diet, Fluid, Activity

7.4.1 Diet and Fluid

7.4.1.1 Part 1

On Day -1 of each cohort, subjects will fast overnight (at least 8 hours) and will continue to fast for 4 hours after Hour 0 for the collection of baseline time-matched HR and BP assessments. On Day 1 of each cohort, subjects will fast overnight (at least 8 hours) before study drug dosing and will continue to fast for an additional 4 hours (after Hour 0) postdose.

On Day 1 of each cohort, meals and snacks must be completed at least 1 hour before any telemetry recording extractions and/or safety ECG.

Normal fluid intake of water is permitted and encouraged, and decaffeinated coffee or tea with nothing added are also permitted. Standard meals will be administered at approximately 4 (lunch), 7 (snack), 10 (dinner), and 13 (snack) hours postdose on Day 1. Standardized meals will be served on all other confinement days.

7.4.1.2 Part 2 and 3

On Day -1 of each cohort, subjects will fast overnight (at least 8 hours) and will continue to fast for 4 hours after Hour 0 for the collection of baseline time-matched HR and BP assessments. On Days 1 and 5 in Part 2, and Days 1, 7, and 14 in Part 3, subjects will fast overnight (at least 8 hours) before the dose and will continue to fast for an additional 4 hours (after Hour 0) postdose.

Normal fluid intake of water is permitted and encouraged, and decaffeinated coffee or tea with nothing added are also permitted. Standard meals will be administered at approximately 4 (lunch), 7 (snack), 10 (dinner), and 13 (snack) hours postdose on dosing days. All meals should be served at approximately the same time each day.

7.4.2 Activity

Subjects will avoid strenuous physical activity (eg, weight lifting, running, bicycling) from 72 hours before admission to the study site, throughout the study (including the washout interval in Part 3), and until after discharge after the last scheduled dose.

7.5 Criteria for Discontinuation or Withdrawal of a Subject

The primary reason for discontinuation or withdrawal of the subject from the study or study drug should be recorded in the electronic case report form (eCRF) using the following categories.

- Pretreatment event or TEAE. The subject has experienced a pretreatment event or AE that requires early termination because continued participation imposes an unacceptable risk to the subject's health or the subject is unwilling to continue because of the pretreatment event or AE.

- Liver function test (LFT) abnormalities.
 - ALT or AST $>3 \times$ ULN in conjunction with elevated total bilirubin $>2 \times$ ULN without findings of cholestasis or other alternate etiology.
- Significant protocol deviation. The discovery that the subject failed to meet protocol entry criteria or did not adhere to protocol requirements, and continued participation poses an unacceptable risk to the subject's health.
- Lost to follow-up. The subject did not return to the clinic and attempts to contact the subject were unsuccessful. Attempts to contact the subject must be documented in the subject's source documents.
- Voluntary withdrawal. The subject (or subject's legally acceptable representative) wishes to withdraw from the study. The reason for withdrawal, if provided, should be recorded in the eCRF.

Note: All attempts should be made to determine the underlying reason for the withdrawal and, where possible, the primary underlying reason should be recorded (ie, withdrawal due to an AE should not be recorded in the "voluntary withdrawal" category). Similarly, lack of efficacy should not be recorded in the "voluntary withdrawal" category.

- Study termination. The sponsor, IRB and/or IEC, or regulatory agency terminates the study.
- Pregnancy. The subject is found to be pregnant. Note: If the subject is found to be pregnant, the subject must be withdrawn immediately.

Note: The specific reasons should be recorded in the "specify" field of the eCRF.

If a subject chooses to withdraw from study participation due to personal concerns related to the COVID-19 pandemic, this should be specified as the reason for subject withdrawal in the eCRF. The reason for discontinuation should be entered on the eCRF including unavoidable circumstances such as the COVID-19 pandemic.

